9.3.2.3 Rate of cinacalcet discontinuation

Refer to definition defined in 9.3.1.3

9.3.2.4 Prescribing patterns of cinacalcet

Treatment patterns of cinacalcet at initiation, immediately prior to hypocalcemia event and after first occurrence of hypocalcemia (e.g. reduced dose or discontinuation of cinacalcet) during the 90 days (or up to 12 months) following hypocalcemia event.

9.3.2.5 Treatment patterns of active vitamin D, phosphate binders and CVD medications

Treatment patterns of active vitamin D, phosphate binders and CVD medications 90 days prior to cinacalcet initiation, immediately prior to cinacalcet initiation, and immediately after first occurrence of hypocalcemia during the 90 days (or up to 12 months) following hypocalcemia event

9.3.2.6 Cinacalcet re-initiation following cinacalcet discontinuation

Patients who discontinued cinacalcet are identified according to 9.3.1.3. Re-initiation of cinacalcet during the 12 months following discontinuation of cinacalcet will be defined as patients who subsequently receive a new prescription. If the duration of a patient first prescription following discontinuation was less than 15 days (2 weeks) and the gap between the end date of that prescription to the start date of the subsequent prescription

was greater than 15 days then the subsequent prescription will be used to identify treatment re-initiation.

9.3.2.7 Kinetics of hypocalcemia events

For the exploratory objectives, the aim is to describe how many patients with more than one episode of hypocalcemia transitioned through the different disease severity stages. The aim is to assess whether hypocalcemia progresses slowly or whether patients tend to fall into the severe range immediately and then resolve or go back and forth.

Patients with more than one hypocalcemia event will be defined as one of the following:

- Progressors – Subsequent events were more severe than initial events
- Remitters - Subsequent events were less severe than initial events
- Fluctuators – events ranged in severity with no trend in one direction

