8.3 Exploratory

- 8.3.1 To explore the number of HD patients who initiate cinacalcet (i.e. first prescription) with hypocalcemia (*Cohort A*)

HD patients with cinacalcet prescription and serum calcium >8.4 mg/dL at baseline

(Cohort B)

- 8.3.2 To explore the incidence of hypocalcemia events among HD patients with cinacalcet prescription according to PTH levels
- 8.3.3 To explore the frequency of hypocalcemia events among HD patients with cinacalcet prescription according to PTH levels

Hypocalcemia HD patients with cinacalcet prescription (Cohort 1)

- 8.3.4 To explore kinetics of hypocalcemia events in cinacalcet patients with more than one episode of hypocalcemia
- 8.3.5 To explore the impact of hypocalcemia treatment on serum calcium level
- 8.3.6 To explore the impact of hypocalcemia cardiovascular events (CVE) or death

9. Research Methods

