9.3.2 Outcome Assessment

Table 1 summarizes the outcomes to be assessed according to each objective.

Table 1. Outcomes for analysis

Objective	Definition
PRIMARY OBJECTIVES	
Hypocalcemia HD patients with cinacalcet prescription	
- Rate of cinacalcet discontinuation	- Number of patients who discontinue cinacalcet. Discontinuation is defined as the time point beyond which there were ≥ 90 consecutive prescription-free days.
-Cinacalcet prescribing pattern	- No change, dose reduced (relative to dose prior to hypocalcemia), discontinued, Dose increased (relative to dose prior to hypocalcemia)
- Prescribing pattern for any treatment and each of the following drugs: paricalcitol, older AVD, phosphate binder, dialysate calcium and CVD medications	- No change, dose reduced (relative to dose prior to hypocalcemia), discontinued, Dose increased (relative to dose prior to hypocalcemia)
SECONDARY OBJECTIVES	
HD patients with cinacalcet prescription	
- Incidence of hypocalcemia	- First occurrence of a serum calcium (< 8.4 vs. ≥ 8.4 mg/dL) - First occurrence of serum calcium defined by severity: mild (serum calcium ≥ 8.0 - < 8.4 mg/dL), moderate (serum calcium ≥ 7.5 - < 8.0 mg/dL), severe (serum calcium < 7.5 mg/dL)
Hypocalcemia HD patients who discontinued cinacalcet prescription	
- Rate of cinacalcet re-initiation	- Number of patients who re-initiate cinacalcet prescription following discontinuation (yes/no)
- Prescribing pattern for each of the following drugs: cinacalcet, paricalcitol, older AVD, phosphate binder, dialysate calcium and CVD medications	- No change, dose reduced (relative to dose prior to hypocalcemia), discontinued, Dose increased (relative to dose prior to hypocalcemia)
EXPLORATORY OBJECTIVES	
- Incidence of hypocalcemia by PTH	- No. of patients with hypocalcemia according to PTH levels: low (< 10 ng/L or pg/mL), normal (10-65 ng/L or pg/mL) or high (> 65 ng/mL or pg/mL)
- Kinetics of hypocalcemia	- Progressors (subsequent events were more severe than initial events), remitters (subsequent events were less severe than initial events), fluctuators (events ranged in severity with no trend in one direction)
- Changes in calcium level	- Changes in mean or median calcium levels following changes in treatment treatment
- Cardiovascular event	- Any coronary artery event (CVE), cerebrovascular event (CVE), peripheral arterial event (PAE), congestive heart failure event (CHFE), or sudden cardiac event (SCE)

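### The kinetics classes in Protocol 9.3.2.7 are bounded by the severity of the first event and never count return to normal calcium, so they cannot say how many patients resolve

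*Protocol*

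**What the plan says.** Protocol 9.3.2.7 sets out to count how patients with repeat episodes move between severity stages. It also asks "whether patients tend to fall into the severe range immediately and then resolve or go back and forth".

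The classification that follows is limited in population and in scale:

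- **Population:** "Patients with more than one hypocalcemia event will be defined as one of the following".
- **Progressors:** "Subsequent events were more severe than initial events".
- **Remitters:** "Remitters - Subsequent events were less severe than initial events".
- **Fluctuators:** "events ranged in severity with no trend in one direction".

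Table 1 in 9.3.2 repeats the same three classes. An event is a serum calcium below 8.4 mg/dL (9.3.1.2). Its severity is mild (8.0 to below 8.4), moderate (7.5 to below 8.0) or severe (below 7.5 mg/dL) (9.3.2.1).

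**The concern.** The section asks a question with a recovery state in it, but the classes have none. Every class compares one low value or episode with another. Mild is the least severe stage available, and severe is the most severe.

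This creates two problems. First, which classes a patient can enter depends on the severity of the first event, before anything later has happened. A table of class counts can then be read as describing the course of calcium when it partly describes where patients started. Second, the pattern of one severe fall followed by recovery is what the aim describes, yet such a patient has one event and is not classified. A patient with two mild events and then normal calcium for the rest of the year is not a remitter. A patient who goes from severe to moderate and stays there is.

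At stake is whether exploratory objective 8.3.4 can answer the question that its own method section poses. Section 9.1 lists calcium recovery among the outcomes that the cohort design is meant to study. Section 7.1 reports that in the cited US study most patients were back at 8.4 mg/dL or above within 90 days. The path left out may therefore be a common one.

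**Working it through.** The protocol gives no figure for this outcome, so there is nothing to reproduce.

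**Step 1: what the definitions allow (no assumptions needed).**

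| First event | Can be a progressor? | Can be a remitter? | Return to 8.4 mg/dL or above counted? |
|---|---|---|---|
| Mild | yes | no (no stage below mild) | no |
| Moderate | yes | yes | no |
| Severe | no (no stage above severe) | yes | no |

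**Step 2: size of the constraint with two events and no trend.** Assume two independent events, each mild, moderate or severe with probability 0.6, 0.3 and 0.1. This mix is an assumption; the documents give none.

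- Mild-first: progressor 0.3 + 0.1 = 40%; remitter 0%.
- Moderate-first: progressor 10%; remitter 60%.
- Severe-first: progressor 0%; remitter 0.6 + 0.3 = 90%.
- All progressors: 0.6 × 0.4 + 0.3 × 0.1 = 0.27.
- All remitters: 0.3 × 0.6 + 0.1 × 0.9 = 0.27.

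The totals balance, but the strata differ sharply although nothing changes over time. With other mixes the totals also balance: 19.8% each at 75/20/5 and 33.3% each at equal thirds.

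**Step 3: three events, same mix.** The text does not say how several later events are compared with the first, so two readings are shown.

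- All later events against the first: progressors 0.6 × 0.4² + 0.3 × 0.1² = 9.9%; remitters 0.3 × 0.6² + 0.1 × 0.9² = 18.9%.
- Worst later event against the first: progressors 0.6 × (1 − 0.6²) + 0.3 × (1 − 0.9²) = 44.1%; remitters 18.9%.

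The direction of the imbalance reverses between the two readings.

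**Step 4: trend-free monthly series.** Simulated calcium was started at 8.4 mg/dL or above (entry to Cohort B, 9.2.2.1) and tested monthly (9.4). Assumed inputs are mean 8.9 mg/dL, SD 0.4 between and 0.5 within patients, with each low value counted as an event. Cells show progressors vs remitters as a percentage of patients with more than one event.

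| Monthly autocorrelation | All later vs first | Last vs first | Worst later vs first |
|---|---|---|---|
| 0 | 7.2 vs 12.7 | 20.9 vs 21.0 | 39.6 vs 12.7 |
| 0.5 | 6.1 vs 8.5 | 19.8 vs 15.9 | 43.3 vs 8.5 |
| 0.8 | 4.0 vs 3.1 | 17.9 vs 6.9 | 42.9 vs 3.1 |

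Six scenarios were run in all (mean 8.7 to 9.0, between-patient SD 0 to 0.4, within-patient SD 0.5 to 0.6, autocorrelation 0 to 0.8). Events were counted as single values or as episodes. Across these:

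- 62% to 93% of patients with more than one event had a mild first event, and none of them was a remitter.
- 18% to 61% of patients with any event had only one, and so fall outside the classification.

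**The case against.** The restriction to repeat episodes is deliberate. Objective 8.3.4 is "To explore kinetics of hypocalcemia events in cinacalcet patients with more than one episode of hypocalcemia", so leaving out single-event patients does not contradict the objective. This stands. The mismatch is narrower: it lies between that restriction and the part of the aim in 9.3.2.7 that asks about resolution.

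Recovery is also shown elsewhere. Section 9.6.2.1 plots the median and interquartile range of calcium over the 12 months after the event. Section 9.6.2.4 plots calcium after the first event by treatment and summarises the average percentage change. This stands in part: both describe the group, and neither counts patients who return to normal, whereas 9.3.2.7 asks how many patients follow each path.

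A SAP may settle how three or more events are compared. That is a fair task for a SAP and is not the point here. The population and the three classes are already fixed in 9.3.2.7 and Table 1. The severity stratification in 9.6.2.6 covers primary and secondary analyses only, so it does not reach this outcome.

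A reader might infer that the floor at mild produces a spurious excess of progressors, so that the study would report progression where there is none. The documents do not support this. Floor and ceiling cancel exactly with two exchangeable events. With more events the direction depends on the comparison rule, which the protocol does not state, and on calcium inputs that it does not give. Under the reading closest to the text, all later events against the first, remitters often lead.

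**Conclusion.** The point holds in a limited form. From the protocol's own definitions, mild-first patients cannot be remitters, severe-first patients cannot be progressors, and return to 8.4 mg/dL or above is never counted. The classes therefore cannot answer the resolution part of the stated aim, and unstratified counts mix the starting severity with the later course. None of this rests on an assumption.

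The sizes do rest on assumptions. The 40% vs 0% and 0% vs 90% splits use a 60/30/10 mix and two independent events. The 62% to 93% mild-first share and the 18% to 61% single-event share come from assumed calcium distributions. No direction or ratio of progressors to remitters should be claimed.

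The consequence is modest: one exploratory, descriptive objective is affected, with no hypothesis test and no bearing on the primary results. The change is worth making because it is cheap.

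**What to change.** In 9.3.2.7 and Table 1:

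1. Keep the three classes for patients with more than one episode, but report them by severity of the first event. Report progression only among patients whose first event was mild or moderate, and remission by stage only among those whose first event was moderate or severe.
2. Add a supplementary table for all of Cohort 1 with a fourth state, normal (8.4 mg/dL or above). Show transitions between successive calcium tests across the four states, by severity of the first event.
3. In that table, give the number who resolved after a single event. Count a patient as resolved only where a later normal value is recorded, so that death, transfer or absence of further tests is not taken for recovery.

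The cost is a few lines of wording and one extra exploratory table from calcium values already in the dataset. The table goes slightly beyond the repeat-episode wording of objective 8.3.4, so it should be labelled supplementary, or the objective widened to match.

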9.3.2.8 Time to cardiovascular events or death

For exploratory objective of CVE and death events following hypocalcemia will be defined by ICD-10 codes in Appendix 1.

9.3.3 Covariate Assessment

Table 2 summarises the covariates to be evaluated. The most proximal values identified at the end of the baseline period will be used in the analysis. Time-varying covariates will be evaluated at consecutive 90 days intervals following the baseline period. Continuous (e.g. laboratory parameters, age, BMI, systolic blood pressure and etc) time varying covariates will be determined at the end of each interval (one value only). Categorical (e.g. concomitant medications, medical events etc) time-varying covariates will be determined by the occurrence of a prescription or event respectively within an interval. During intervals where an event of interest occurs, only data prior to the event will be used in the corresponding time-varying analysis (most recent value prior to the event for continuous covariates and vascular access). The presence (combined therapy) or absence of alternative therapeutic class (AVD for the cinacalcet-related analysis; cinacalcet for the AVD-related analysis) will be integrated as a covariate. For the exposure period pre-KDIGO covariate if the baseline period or the interval corresponding to the time-varying analysis included the date of the publication of the KDIGO guidelines, then the value of this covariate will be set to Yes.

Table 2: Baseline and time-varying covariates

Parameter type	Covariate	Categories	Variable type in time-varying analysis
Demographics	Age	<30, 30-49, 50-64, 65+	baseline
	Gender	Male/female	baseline
	Country		baseline
	Exposure period pre-KDIGO*	Yes/No	time-varying
	Mean time of follow-up following cinacalcet initiation		
Clinical	Hospitalisation	Yes/No	time-varying
	BMI	<18.5, 18.5-<25, 25-<30, ≥30	baseline
	Pre-dialysis systolic blood pressure [mm Hg]	<120; 120-<130; 130-<140; 140-<160; 160+	time-varying
	Smoking status	Current, Former, Non-smoker	baseline
Medical history	CKD aetiology	Hypertension / vascular, Glomerulonephritis, Diabetes, Tubulo-interstitial, Polycystic Kidney Disease, Invalid/Missing, Unknown	baseline
Medical events	Diabetes	Yes/No	baseline
	Cancer	Yes/No	baseline
	CVD	Yes/No	time-varying
	Fracture	Yes/No	time-varying
Dialysis parameters	Vascular access	Catheter vascular access only, Non-catheter vascular access only, Missing	baseline
	Dialysis vintage	Continuous	time-varying
	Calcium dialysate concentration [mEq/L]	<2.5, ≥2.5	time-varying
	Net Ultrafiltration [L]	Quartiles	baseline
	Actual blood flow [mL/min] *	Quartiles	baseline
Laboratory parameters	Hemoglobin [g/dL]	<10, 10-<12, ≥12	baseline
	Ferritin [µg/L]	<500, ≥500	baseline
	CRP [mg/L] *	Quartiles	baseline
	Serum albumin [g/L] *	Quartiles	time-varying
	Creatinine [µmol/L] *	Quartiles	baseline
	Total calcium [mmol/L]	<2.10, 2.10-2.37, >2.37	time-varying
	Phosphate [mmol/L]	<1.13, 1.13-1.78, >1.78	time-varying
	Alkaline phosphatase	<44 IU/mL, 44-147 IU/mL (normal), >147	time-varying

	PTH [pg/mL]	<150, 150-<300, 300-<600, ≥600	time-varying
Medication use	Cinacalcet use [§]	Yes/No	time-varying
	Paricalcitol use [§]	Yes/No	time-varying
	Older AVD use [§]	None; Alfacalcidol; Calcitriol; both	time-varying
	Phosphate binder use [§]	None, Only calcium-based, Only non calcium-based, Any	time-varying
	Cardiovascular medication [§]	Yes/No	time-varying

01 August 2009. If the baseline period or the interval corresponding to the time-varying analysis includes the publication of the KDIGO guidelines, then the value of the value of exposure period pre-KDIGO covariate will be set to Yes; [§] relevant ATC codes in Appendix B; ^{} The quartiles' cut-offs for these variables will be derived at baseline.

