8.1 Primary

Hypocalcemia HD patients with cinacalcet prescription (Cohort 1)

- 8.1.1 To determine the rate of cinacalcet discontinuation following hypocalcemia event
- 8.1.2 To describe prescribing patterns of any treatment intervention (e.g. vitamin D, phosphate binders and cardiovascular disease (CVD) medications) prior to cinacalcet initiation, at time of cinacalcet initiation and after hypocalcemia event
- 8.1.3 To describe time to any treatment intervention and treatment patterns (e.g. vitamin D, phosphate binders and cardiovascular disease (CVD) medications) prior to cinacalcet initiation, at time of cinacalcet initiation and after hypocalcemia event
- 8.1.4 To identify factors associated with changes to any treatment intervention following a hypocalcemic event

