9.4 Data Sources

An extensive medical record for each haemodialysis patient, essential to their clinical care and encompassing general information, past medical history, physiological anamnesis, comorbidities, allergies, amputations, transfusion history, current medication, laboratory tests, vaccination status, residual renal function, dialysis access, surgery (including parathyroidectomy) and transplantation, is captured directly in the EuCliD system on admission to an FMC facility. These data are reflected in AROii.

Demographic and clinical characteristics include age, gender, height, weight, mobility, marital status, education level, occupational status, smoking history, CKD etiology (coded according to ICD-10) and RRT initiation (country, center, modality and date). Detailed records on patient medical history were used to confirm history of cardiovascular disease, cerebrovascular disease, malignancy and diabetes. Information captured on HD therapy includes dialysis vintage, vascular access type and duration of placement, number of treatments per week, duration of treatment, actual blood flow, dialysis adequacy (Kt/V) as well as pre- and post-dialysis weight. Hospitalization data

including admission and discharge dates and ICD-10 codes, and death data, are routinely captured by all FMC sites.

Descriptive information on prescribed medications includes product (description and ATC code), start and end dates of prescription, dose and administration route. Laboratory data, including markers for anaemia, bone and mineral metabolism, inflammation and nutrition, reflects normal clinical care in terms of testing frequency. Specific to this study, calcium and phosphorous are typically tested on a monthly basis, whilst PTH is tested quarterly.

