9.6.2.2 Analysis of the Primary, Secondary and Exploratory Endpoint(s)

9.6.2.3 Primary and secondary objective endpoints

Point estimates and 95% confidence intervals will be derived to determine the rate of hypocalcemia following cinacalcet initiation, rate of cinacalcet discontinuation following hypocalcemia event and rate of cinacalcet re-initiation following discontinuation due to hypocalcemia.

Time to first hypocalcemia event, time to any treatment intervention following hypocalcemia event, and time to cinacalcet re-initiation will be estimated using Kaplan-Meier methods according to baseline calcium levels (i.e. mild, moderate or severe) at baseline.

Cox regression models will be used to identify baseline covariates (Table 2) associated with time to first occurrence of hypocalcemia during the first 12 months of the study, time to any treatment intervention during the 12 months following hypocalcemia event and time to cinacalcet re-initiation during the 12 months following cinacalcet discontinuation. Subjects who do not experience hypocalcemia will be censored (according to 9.2.4.1 criteria). Univariate analysis will be performed. Variables significant at the 0.25 level in univariate analysis will be entered into a multivariate analysis using a stepwise regression technique (significance levels of 0.10 for inclusion/exclusion). Hazard ratios and 95% confidence intervals will be presented.

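### Table 2 gives the Cox models only a Yes/No cinacalcet term, nearly constant at baseline, so they cannot show whether prescribed dose is associated with any of the three outcomes

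*Protocol*

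**What the plan says.** Three objectives ask for predictors. Objective 8.1.4, a primary one, is worded "To identify factors associated with changes to any treatment intervention following a hypocalcemic event". Objective 8.2.5 concerns time to hypocalcemia in Cohort B, and 8.2.8 concerns time to re-initiation in Cohort C.

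Section 9.6.2.3 sets the method: "Cox regression models will be used to identify baseline covariates (Table 2) associated with time to first occurrence of hypocalcemia". The same sentence covers time to any treatment intervention and time to re-initiation. Candidates pass a univariate screen at 0.25 and then stepwise selection at 0.10.

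Table 2 in section 9.3.3 lists the candidates with their categories. Its one cinacalcet row is "Cinacalcet use", Yes/No, labelled time-varying. There is no row for dose. The covariate list in the abstract likewise names cinacalcet only under medication use. For baseline values, section 9.3.3 says "The most proximal values identified at the end of the baseline period will be used in the analysis". For medication and other categorical terms it says that "time-varying covariates will be determined by the occurrence of a prescription or event respectively within an interval".

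Dose is in the data. Section 9.4 states: "Descriptive information on prescribed medications includes product (description and ATC code), start and end dates of prescription, dose and administration route". Section 9.3.4 includes dosage among the prescription fields that were checked and reports more than 99.9% of prescriptions validated. Table 1 sorts cinacalcet prescribing after hypocalcemia by comparison with the dose before it.

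**The concern.** Every patient in Cohorts B, 1 and C has started cinacalcet, so whether the drug was used separates patients very little. What differs between them is how much was prescribed. A screen that offers ferritin, blood flow and ultrafiltration volume as candidates, but not the dose of the study drug, leaves an obvious gap in a study of hypocalcemia on that drug and of the response to it.

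Three questions go unanswered: whether starting dose is associated with time to hypocalcemia, whether the dose in use when calcium fell is associated with a change of treatment, and whether the last dose before stopping is associated with restarting. PTH, calcium and active vitamin D use are candidates and may be related to dose. If so, their hazard ratios could partly reflect it, though the protocol gives nothing from which to judge how far.

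**Working it through.** **1. Does the term vary at baseline?** The baseline periods in section 9.2.3 can be set beside the coding rules in section 9.3.3.

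| Cohort | Baseline period | Value at its end | Exceptions |
|---|---|---|---|
| B | 90 days before initiation | No for essentially all | A short first prescription disregarded under 9.3.1.1 may fall in the window |
| 1 | Initiation to hypocalcemia | Yes for nearly all, since every patient has a prescription in the period | A patient who stopped before the low calcium may be No |
| C | Hypocalcemia to the ascribed stopping date | Discontinued for all | None evident |

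**2. Does it vary after baseline?** The row is labelled time-varying, so this matters if a time-varying model is also fitted.

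- Cohort B: section 9.2.4.1 does not censor patients for stopping cinacalcet, so the term could change to No. Section 9.3.2.1 counts only patients with current supply as at risk, which would hold it at Yes, but that rule is written for monthly cumulative incidence.
- Cohort 1: the term could change if a change in cinacalcet does not itself count as a treatment intervention. The protocol leaves this unclear.
- Cohort C: section 9.3.3 says "During intervals where an event of interest occurs, only data prior to the event will be used", so the term stays No until re-initiation, which is the outcome.

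In each case the variation is on/off status. None of it carries dose.

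**3. What does a near-constant term contribute?** For a binary covariate in a Cox model, information is approximately events × p × (1 − p), where p is the share coded Yes.

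- Event count, for illustration: section 9.5 gives about 1245 cinacalcet patients and 47% with hypocalcemia. 1245 × 0.47 = 585, which the protocol rounds to about 600. Its half width reproduces: 1.96 × √(0.25/600) = 0.040. The point does not rest on these figures. Because the eligibility rules will remove some of the 1245, 585 is probably on the high side.
- At p = 0 or p = 1: 585 × 0 × 1 = 0, so no hazard ratio can be estimated. Near those limits the information is close to zero.
- If dose were split 50:50 (an assumption, as the protocol gives no dose distribution): 585 × 0.5 × 0.5 = 146.25. For a hazard ratio of 1.3, √146.25 × ln 1.3 − 1.96 = 12.09 × 0.262 − 1.96 = 1.21, giving power of about 0.89.
- If dose were split 20:80 (also an assumption): 585 × 0.2 × 0.8 = 93.6. Then 9.67 × 0.262 − 1.96 = 0.58, giving power of about 0.72.

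On these assumptions a dose term would be informative in Cohort B where the present baseline term is close to uninformative.

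**4. Does the row serve another purpose?** Section 9.3.3 names active vitamin D as the alternative-class covariate for a cinacalcet analysis, and cinacalcet as the one for a vitamin D analysis. Section 8 contains no vitamin D analysis, so the row has no evident role in these three models.

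**The case against.** A reader might infer that the term takes one value for every patient and carries no information in any cohort. The documents do not support that. The row is labelled time-varying, Cohort B is not censored on stopping, the current-supply rule is not cited for the Cox models, and nothing requires a Cohort 1 patient to be on drug when calcium falls. On/off status can vary, and only near-constancy in the baseline models is shown.

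A term that is constant also does no harm by itself. It would fail the 0.25 univariate screen and drop out without biasing anything. That stands: the fault lies in what is absent from Table 2.

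Dose is not ignored either. Section 9.3.2.4 and Table 1 describe cinacalcet prescribing around the event, the study tests no formal hypothesis, and no objective asks for a dose-response. This is fair, but those descriptions do not put dose into a predictor model, and three objectives do ask for associated factors.

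The statistical analysis plan is not at hand and may add dose. The protocol nevertheless fixes both the candidate list and its coding, and dose is in neither.

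Finally, dose follows PTH and calcium. A time-updated dose would respond to earlier calcium and could look protective if it is cut as calcium falls. That is a good reason to confine the change to baseline dose.

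**Conclusion.** The point holds for the baseline-covariate Cox models of section 9.6.2.3. Their only cinacalcet term is nearly constant at the end of each baseline period and, where it varies, shows on/off status alone. They cannot show whether prescribed dose is associated with hypocalcemia, treatment change or re-initiation. One primary objective (8.1.4) and two secondary objectives (8.2.5, 8.2.8) are affected. The primary discontinuation estimate is not.

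This rests on reading Table 2 as the full candidate list, as section 9.6.2.3 does, and on the baseline definitions in section 9.2.3. The absence of a dose row is certain. A reader might go further and conclude that the other hazard ratios are biased. The protocol gives no dose distribution and no link between dose and the other covariates, so the size of any distortion cannot be derived. The power figures above are illustrations under assumed splits.

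**What to change.** Add one row to Table 2: prescribed cinacalcet daily dose, from the prescription record, as a baseline candidate under the existing screen and stepwise procedure. Define it by cohort:

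- Cohort B: the dose of the initiating prescription as identified under section 9.3.1.1.
- Cohort 1: the most recent dose on or before the first calcium below 8.4 mg/dL, with on/off supply on that date kept as a separate indicator.
- Cohort C: the last dose before discontinuation.

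Drop the Yes/No term from any model in which it does not vary.

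The cost is one derived variable from data already held and one more candidate in the screen. Because dose is titrated to PTH and calcium, its hazard ratio must be reported as an association only. Time-updated dose and forced entry are optional and not part of this change: the first is affected by earlier calcium and PTH, and the second departs from the stated selection rule. The change concerns a model covariate and implies nothing about how cinacalcet should be dosed.
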